**6. STUDY SYNOPSIS**

TITLE:	A multicenter, open-label, long-term, safety, tolerability and efficacy study of retigabine in adult epilepsy patients with partial-onset seizures (Extension of Study VRX-RET-E22-302)
PHASE:	3
OBJECTIVES:	
 
1. Primary: To evaluate the safety and tolerability of long-term therapy with retigabine administered as adjunctive therapy in adult epilepsy patients with partial-onset seizures, who completed the double-blind Study VRX-RET-E22-302.
 
2. Secondary: To evaluate efficacy of long-term treatment with retigabine and patient quality of life, evaluated through the QOLIE-31-P questionnaire.
 

STUDY DESIGN:	This is an open-label extension study of the placebo-controlled, double-blind Study VRX-RET-E22-302. Patients will be treated with 600-1200 mg/day of retigabine as an adjunct therapy to their current antiepileptic medications (AEDs) or vagal nerve stimulation as established in Study VRX-RET-E22-302. Treatment will be continued until retigabine is approved and commercially available, or until the program is discontinued, followed by a 3-week tapering period and a 30 day post study period for collection of Adverse Events (AEs).
SAMPLE SIZE:	All patients who complete Study VRX-RET-E22-302 are qualified to participate (up to approximately 510 patients).
NUMBER OF SITES:	This is a multicenter study involving approximately 55-60 study sites in the Western, Central, and Eastern Europe, Australia, Israel, South Africa and the United States.
TREATMENT GROUPS:	All patients will be treated with 600-1200 mg/day of retigabine as an adjunct therapy to their current antiepileptic medications (AEDs) or vagal nerve stimulation.
TREATMENT DURATION:	This study will allow the patients who complete Study VRX-RET-E22-302 to continue with retigabine until the drug is approved and commercially available, or until the program is discontinued.
FORMULATION:	Retigabine will be supplied by Valeant Pharmaceuticals, North America in bottles containing tablets in relevant strengths: 50 mg, 100 mg, or 300 mg.

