## **11. STATISTICAL MEASUREMENTS, EVALUATIONS AND ANALYTICAL METHODS**

### **11.1. Assessment of Efficacy**

Monthly total seizure rates will be calculated for the entire open-label part of Study VRX-RET-E22-304 and described statistically. Monthly total seizure rates observed during the open-label extension period will be compared to the monthly total seizure rates observed during the Baseline phase of the double-blind study VRX-RET-E22-302. The percent change in monthly total seizure rates from the Baseline phase will be classified into <0, [0, 25), [25, 50), [50, 75), [75, 100] and described. The responder rate during the open-label study (defined as a reduction in seizure frequency  $\geq 50\%$ ) will also be summarized using descriptive statistics.

The number of seizure free days, in percent to the individual duration of the open-label treatment, will be calculated and summarized using descriptive statistics. This percentage will be classified into [0, 25), [25, 50), [50, 75), [75, 95), [95, 100), [=100] and described statistically.

All-cause withdrawal rates will be calculated as a percentage and respective "times to event" will be described by a Kaplan-Meier survival curve. Specific reasons for withdrawal will also be described separately.

This is an open-label extension study with the emphasis on safety. Efficacy is not the primary objective of this study unlike the double-blind study VRX-RET-E22-302. Descriptive statistics of efficacy measures such as number of patients, mean, standard deviation, median, minimum and maximum will be provided for continuous variables. The number and percentages in each category will be presented for categorical data. The pairwise t-test will be used to assess whether the retigabine treatment remains effective in the open-label extension study if necessary. The pairwise t-test may be sorted by the geographic region [Central/Eastern Europe vs. Rest of World (ROW)]. The safety assessments will use essentially the same descriptive statistics and pairwise t-test as mentioned above for efficacy. The complete details of efficacy analyses will be described in the Statistical Analysis Plan.

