Besides descriptive statistics of the safety evaluations will be presented, the incidence of TEAEs will be compared across treatment group using Fisher's Exact test, only for those events with an incidence of  $\geq 5\%$  over all treatment groups. Fisher's Exact test will be applied if necessary for other safety evaluations (vital signs, physical and neurological examinations, laboratory variables, etc.). QTc interval prolongations will be examined by using both Bazett's and Fridericia's QT correction formulas. The complete details of safety analyses will be described in the Statistical Analysis Plan.

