#### 4.5.5 Vital Signs, Physical Findings and Other Observations Related to Safety

##### 4.5.5.1 Vital Sign Measurements

Vital sign measurements, including supine and standing measurements of systolic blood pressure (mmHg), diastolic blood pressure (mmHg), pulse (bpm), weight (kg), and oral

temperature (°C), are collected at each visit during the open-label extension with the exception of the haematological evaluation visits (Months 2, 4, 8 and 10).

Descriptive statistics for vital sign results and change from baseline for each visit will be presented.

The number of patients with orthostatic hypotension will also be presented. Orthostatic hypotension is defined as either a systolic blood pressure decrease of  $\geq 20$  mmHg upon standing or a diastolic blood pressure decrease of  $\geq 10$  mmHg upon standing.

A by-patient listing of all vital sign measurements will also be provided.

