#### 4.5.5.3 Physical and Neurological Examination

A complete physical examination and complete neurological examination was performed at baseline and at Months 12, 24, and 36. Brief neurological examinations were also performed at all other visits during the open-label extension.

For the 15 items of complete physical exam and 42 items of complete neurological exam, the number and percentage of patients with normal or abnormal results will be presented.

A by-patient listing of physical and neurological examination data will also be provided.

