#### 4.5.5.4 AUA Symptom Index

An AUA Symptoms Index, a 7-item Likert-scored scale describing urinary bladder function, is completed by the investigator at the baseline phase, and at Months 1, 3 and 12.

Descriptive statistics (n, mean, std, median, minimum, maximum) of the AUA symptom index scores in each treatment group will be presented by two table layouts: 1) AUA raw overall scores at baseline, Months 1, 3 and 12, 2) change from baseline to Month 1, 2 and 12.

Besides the descriptive statistics tables, AUA symptom index scores will be categorized by using 3 levels: 0-7 as mild, 8-19 as moderate, and >19 as severe. A shift table of the number (%) of patients in the categories of mild, moderate, and severe will be provided.

A listing of AUA symptom index data will be provided.

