**CONFIDENTIAL**

RM2009/00475/00  
VRX-RET-E22-304

---

Program Path/sas program name

Run Date:

---

Filename: 87272\_304\_SAP\_v2\_final

page 68 of 148

Valeant Pharmaceuticals North America  
 Protocol Number: VRX-RET-E22-304

PAGE X OF X

TABLE 33 NUMBER (%) OF PATIENTS WITH ABNORMAL RESULTS OF PHYSICAL EXAMINATIONS  
 SAFETY POPULATION

TIMEPOINT	PHYSICAL EXAMINATION		RETIGABINE (N=XXX)
BASELINE	SKIN	NORMAL	xx (xx.x%)
		ABNORMAL	xx (xx.x%)
	HEAD	NORMAL	xx (xx.x%)
		ABNORMAL	xx (xx.x%)
	EYES	NORMAL	xx (xx.x%)
		ABNORMAL	xx (xx.x%)
	EARS	NORMAL	xx (xx.x%)
		ABNORMAL	xx (xx.x%)
	NOSE	NORMAL	xx (xx.x%)
		ABNORMAL	xx (xx.x%)
	THROAT	NORMAL	xx (xx.x%)
		ABNORMAL	xx (xx.x%)
	MOUTH	NORMAL	xx (xx.x%)
		ABNORMAL	xx (xx.x%)
	NECK	NORMAL	xx (xx.x%)
		ABNORMAL	xx (xx.x%)
	CHEST	NORMAL	xx (xx.x%)
		ABNORMAL	xx (xx.x%)
	HEART	NORMAL	xx (xx.x%)
		ABNORMAL	xx (xx.x%)

REPEAT FOR TIMEPOINTS MONTH 12, MONTH 24 AND MONTH 36

Program Path/sas program name

Run Date:

Valeant Pharmaceuticals North America  
 Protocol Number: VRX-RET-E22-304

PAGE X OF X

TABLE 33 NUMBER (%) OF PATIENTS WITH ABNORMAL RESULTS OF PHYSICAL EXAMINATIONS  
 SAFETY POPULATION

TIMEPOINT	PHYSICAL EXAMINATION		RETIGABINE (N=XXX)
BASELINE	LUNGS	NORMAL	xx (xx.x%)
		ABNORMAL	xx (xx.x%)
	BREAST	NORMAL	xx (xx.x%)
		ABNORMAL	xx (xx.x%)
	ABDOMEN	NORMAL	xx (xx.x%)
		ABNORMAL	xx (xx.x%)
	GENITALIA	NORMAL	xx (xx.x%)
		ABNORMAL	xx (xx.x%)
	EXTREMITIES	NORMAL	xx (xx.x%)
		ABNORMAL	xx (xx.x%)
	OTHER	NORMAL	xx (xx.x%)
		ABNORMAL	xx (xx.x%)

REPEAT FOR TIMEPOINTS MONTH 12, MONTH 24 AND MONTH 36

71

Program Path/sas program name

Run Date:

Valeant Pharmaceuticals North America  
 Protocol Number: VRX-RET-E22-304

PAGE X OF X

TABLE 34 NUMBER (%) OF PATIENTS WITH ABNORMAL RESULTS OF NEUROLOGICAL EXAMINATIONS  
 SAFETY POPULATION

TIMEPOINT		RETIGABINE (N=XXX)
BASELINE	NEUROLOGICAL EXAMINATION - COMPLETE	
	GENERAL	
	LEVEL OF CONSCIOUSNESS	NORMAL xx (xx.x%) ABNORMAL xx (xx.x%)
	LEVEL OF APPEARANCE/MOTOR EXPRESSION	NORMAL xx (xx.x%) ABNORMAL xx (xx.x%)
	MENTAL STATUS	NORMAL xx (xx.x%) ABNORMAL xx (xx.x%)
	SPEECH	NORMAL xx (xx.x%) ABNORMAL xx (xx.x%)
	CRANIAL NERVES	
	VISION	NORMAL xx (xx.x%) ABNORMAL xx (xx.x%)
	EYE MOVEMENTS	NORMAL xx (xx.x%) ABNORMAL xx (xx.x%)
	JAW MOVEMENT AND FACIAL SENSATION	NORMAL xx (xx.x%) ABNORMAL xx (xx.x%)
	FACIAL MOTOR	NORMAL xx (xx.x%) ABNORMAL xx (xx.x%)
	SWALLOWING, PHARYNX, LARYNX	NORMAL xx (xx.x%) ABNORMAL xx (xx.x%)

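### SAP Tables 32 to 34 show only net change: no summary of orthostatic hypotension or of the examinations counts patients who went from normal to abnormal

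*Protocol*

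**What the plan says.** - Single group. Protocol synopsis, Treatment Groups: "All patients will be treated with 600-1200 mg/day of retigabine as an adjunct therapy". The safety table shells have one retigabine column.
- Examinations. SAP 4.5.5.3: for the 15 physical and 42 neurological items, "the number and percentage of patients with normal or abnormal results will be presented". The Table 33 shell gives a Normal/Abnormal block at baseline with the instruction "REPEAT FOR TIMEPOINTS MONTH 12, MONTH 24 AND MONTH 36". Table 34 does the same for the complete and brief neurological examinations.
- Orthostatic hypotension. SAP 4.5.5.1: "The number of patients with orthostatic hypotension will also be presented". Table 32 gives N, Yes and No at each time point.
- Denominator. SAP 4.3 bases each percentage on the patients providing data at that time point. Protocol 11.4.2 imputes no safety data apart from incomplete adverse event onset dates.
- Elsewhere in the SAP. For the AUA index, 4.5.5.4 plans the paired layout: "A shift table of the number (%) of patients in the categories of mild, moderate, and severe will be provided" (Table 38). Table 29 categorises QTc change from baseline.
- Testing. Protocol 11.2 first states that these other evaluations, examinations included, are analysed descriptively. It then says that "the incidence of TEAEs will be compared across treatment group using Fisher's Exact test" and goes on: "Fisher's Exact test will be applied if necessary for other safety evaluations (vital signs, physical and neurological examinations, laboratory variables, etc". Protocol 11.1 adds: "The safety assessments will use essentially the same descriptive statistics and pairwise t-test as mentioned above for efficacy". The SAP names no test for any of them.
- Baseline. Protocol 10.1 and 10.5, and the first footnote to SAP Table 1, set the extension baseline at Visit 9 of Study 302, the end of double-blind maintenance. SAP 4.2 uses the last value before Study 302 treatment for baseline characteristics. SAP 4.5.5.1 and 4.5.5.3 do not say which applies.

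**The concern.** Long-term safety and tolerability is the primary objective. Protocol 7.5 reports that the commonest adverse events are CNS-related and dose-dependent, among them abnormal gait, tremor, ataxia and abnormal vision. The neurological examination is the scheduled objective check on such effects.

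In a single-group study, the question a reader brings to Tables 32 to 34 is how many patients without the abnormality at baseline acquired it on retigabine. Separate visit percentages do not answer that, for two reasons. New and resolved abnormalities offset each other, so only the net difference shows. The set of patients also changes from visit to visit, so the percentage can move although nobody's status changed, or stay still because those who worsened have left. Withdrawal for an intolerable adverse event is allowed (Protocol 10.20.1), so loss linked to abnormal findings is plausible.

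**Working it through.** The documents give no abnormality rates, no sample size calculation and no power for these variables, so there is no planned figure to reproduce. All rates below are assumptions chosen to show the mechanism.

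**1. Cancellation.** Let N be the patients with both assessments, B those abnormal at baseline, w the newly abnormal and r the resolved.

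- Displayed later rate = (B − r + w)/N. Newly abnormal among baseline-normal = w/(N − B).
- With N = 300, B = 60, w = 24, r = 24: baseline 60/300 = 20.0%; later (60 − 24 + 24)/300 = 20.0%; newly abnormal 24/240 = 10.0%.
- Range: with w = r, anything from 0 to 60 gives the same two margins. An unchanged 20.0% is therefore compatible with 0/240 = 0% up to 60/240 = 25% of baseline-normal patients becoming abnormal.

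**2. Dropout with no change in anyone.** Let a and b be the dropout proportions among abnormal and normal patients.

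- Displayed rate = B(1 − a)/[B(1 − a) + (N − B)(1 − b)].
- a = 40%, b = 20%: 36/(36 + 192) = 36/228 = 15.8%.
- a = b: 20.0%.
- a = 20%, b = 40%: 48/(48 + 144) = 48/192 = 25.0%.

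**3. Why a shift table by visit is not enough.** Take N = 510 (the approximate upper limit in the synopsis) and 51 abnormal at baseline (10.0%). Assume 18% dropout, the six-month figure that Protocol 7.4 gives for the earlier extension study, so about 92 leave and 418 stay. Suppose 40 baseline-normal patients become abnormal, have this recorded, and leave, together with 9 who were abnormal at baseline.

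- Visit percentage: (51 − 9)/418 = 42/418 = 10.0%, the same as baseline.
- Shift at that visit among those still present: baseline-normal patients remaining = 418 − 42 = 376, newly abnormal 0/376.
- Shift to the worst on-treatment assessment: 40/459 = 8.7%.

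Only the last of these counts the patients who worsened and left.

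**4. Which baseline.** Protocol 7.1 describes Study 302 as 900 mg/day and 600 mg/day against placebo. At Visit 9 the two active arms had already been through titration and 12 weeks of maintenance on retigabine. An abnormality that arose in that period counts as baseline-abnormal under a Visit 9 baseline and as new under a pre-treatment baseline. For former placebo patients, both baselines precede retigabine.

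**The case against.** The tempting stronger reading is that the plan will run Fisher's exact test on baseline against later visits in the same patients, as if they were independent groups, and so lose power to detect worsening. The documents do not support it. The Fisher sentence in Protocol 11.2 follows directly on a comparison across treatment groups, applies only if necessary, and comes after a statement that these evaluations are descriptive. The SAP, to which the protocol defers the details, contains no test. Between the former Study 302 arms the patients are different people and Fisher's test would be valid. Nor would a paired test cure cancellation: with 24 new and 24 resolved, exact McNemar gives p = 1.

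The other objections carry some weight:

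- New or worsened adverse events are counted per patient by preferred term, severity and relationship (SAP 4.5.2), and the protocol's definition of an adverse event includes unfavourable signs. Clinically significant vital signs must be reported as adverse events (Protocol 10.3.1). This holds, but 10.3.2 has no such rule for examination findings, and the route runs through investigator judgement.
- Listings 26 to 28 show individual results. However, Listings 27 and 28 are titled as abnormal results only, so a patient with no baseline row may have been normal or not examined.
- Early leavers return for a full examination (Protocol 9.7.5 and 10.20). That visit follows a three-week taper whose third week is without study drug (10.16), and the table shells have no row for it.
- Volume. From the shells, 42 complete items at 3 visits and 13 brief items at 8 visits give 126 + 104 = 230 neurological item-by-visit shifts. Physical items add 15 × 3 = 45 and orthostatic hypotension 11, in total 286. This is a fair reason to be selective and to keep the tables free of tests.

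**Conclusion.** The point holds as a matter of presentation. Tables 32, 33 and 34 can show only net change in a changing set of patients, and no examination or orthostatic hypotension summary counts those who worsened. The SAP already uses the paired layout for the AUA index, so its absence here is an inconsistency that is easily removed.

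The true size cannot be stated, because the documents give no rates. Under the assumed 20% baseline abnormality, an unchanged margin is compatible with anything from 0% to 25% of baseline-normal patients becoming abnormal. The dropout patterns tried move the displayed rate between 15.8% and 25.0% with no change in anyone.

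Nothing is lost from the data, since listings, adverse event tables and the final visit remain. A reader should not infer that an invalid test is planned or that study power is affected. The label is a cheap improvement.

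**What to change.** - In SAP 4.5.5.1 and 4.5.5.3, add shift-from-baseline tables in the layout of Table 38 for orthostatic hypotension and for the physical and neurological examinations. Show the number and percentage of baseline-normal patients who become abnormal, at each visit where the item is assessed.
- Add rows for the worst and the last on-treatment assessment. Take in unscheduled and early-termination assessments so that patients who later leave are counted, and mark those made after taper as such.
- State which baseline is used: Visit 9 of Study 302 or the last value before Study 302 treatment. Present results by former Study 302 arm, or against both baselines.
- To contain the output, limit the neurological tables to body-system groups or to the CNS-relevant items. Keep them descriptive.
- Optionally, clarify in Protocol 11.2 that Fisher's exact test applies only between different patients, for example the former Study 302 arms, and not to baseline-versus-visit comparisons.

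The cost is SAP wording, a few more table programs and a longer output set. No new visits, procedures or patients are needed.

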## 11.3. Determination of Sample Size

Not applicable for this long-term extension study.

## **11.4. Additional Statistical Considerations**

### **11.4.1. Analysis Population**

The safety population will include all patients who successfully complete the Transition phase of Study VRX-RET-E22-302 and were included in this long-term study. The Transition phase is the phase of Study VRX-RET-E22-302 during which patients were adjusted to a 300 mg TID dose. No other population for analysis is defined for this long-term extension.

### **11.4.2. Handling of Missing Data**

No imputation will be made for missing data in the safety analyses, with the exception of incomplete date variables regarding adverse events onset date that is necessary for defining treatment-emergent adverse events. More details on imputation of partial dates will be provided in the statistical analysis plan.

## **12. ADVERSE EVENTS**

An adverse event (AE) is defined as any untoward clinical occurrence in a patient administered a pharmaceutical drug product that does not necessarily have a causal relationship with the study drug. An AE can therefore be any unfavorable and unintended sign (including an abnormal laboratory finding), symptom or disease temporarily associated with the use of a drug product, whether or not related to the drug product.

The presence or occurrence of any of those clinical manifestations and/or alterations in clinical laboratory test results that are either present before participation in this study or that are part of the normal fluctuations or progression of their pre-study health state, will not engender an AE report to the health authorities. Clinical manifestations and/or abnormal laboratory values measured during the study that are a sign of worsening of the patient's pre-study health status or that are new findings may, if clinically relevant, be an AE reportable to the health authorities. Abnormal laboratory values represent adverse events when they are indicative of a disease or defect (e.g., reduced hematocrit resulting in anemia), necessitate intervention (e.g., administration of packed red blood cells or other therapies), or result in dose reduction or permanent discontinuation of the drug product.

Throughout the course of the study, AEs will be monitored and recorded on the patients' source documents and CRFs. The onset, seriousness, intensity, duration, actions taken, effect on study drug administration (e.g., discontinuation), the potential relationship to the study drug, as well as the date of resolution, if any, will be recorded.

## 12.1. Definition and Grading Intensity

### Serious Adverse Events

A serious adverse event (SAE) is an event that results in any of the following outcomes:

- Death.
- Life-threatening adverse experience.
- Hospitalization (unplanned hospital stay) or prolongation of existing hospitalization.
- Persistent or significant disability/incapacity.
- Congenital anomaly/birth defect.

Important medical events that may not result in death, be life-threatening or require hospitalization may be considered serious adverse events when, based on appropriate medical judgment, they may jeopardize the subject and may require medical or surgical intervention to prevent one of the outcomes listed above.

Planned hospitalization or surgery for a condition present prior to the participant's enrollment in the study will not meet the definition of an SAE.

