4.5.3 Deaths, Serious Adverse Events, and Other Significant Adverse Events

A serious adverse event (SAE) is any AE occurring at any dose that results in any of the following outcomes:

- Death
- Is a life-threatening experience. Life-threatening means that the patient was, in the view of the investigator, at immediate risk of death from the event as it occurred
- Requires in-patient hospitalization or prolongation of existing hospitalization. Hospitalization for elective treatment or a pre-existing condition that did not worsen during the clinical investigation is not considered an AE.
- Results in a persistent or significant disability/incapacity (i.e., a substantial disruption of a person’s ability to conduct normal life functions). Disability is defined as a substantial disruption in a person’s ability to conduct normal life functions
- Results in a congenital anomaly/birth defect

Important medical events that may not result in death, be life threatening, or require hospitalization may be considered SAEs only when they jeopardize the health of the patient or require medical or surgical intervention to prevent one of the outcomes listed in the above definition. If there is any doubt whether the information constitutes an SAE, the information is treated as an SAE in this study.

The following adverse event summaries will be provided:

- A summary of the number and percentage of patients reporting a fatal treatment emergent adverse event by body system, and preferred term
- A summary of the number and percentage of patients reporting a serious treatment emergent adverse event by body system, and preferred term
- A summary of the number and percentage of patients reporting a treatment emergent adverse event leading to withdrawal from the study by body system and preferred term

The following adverse event listings will also be provided:

- A by-patient listing of all deaths that occurred during the study
- A by-patient listing of all serious adverse events
- A by-patient listing of all adverse events leading to withdrawal

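### The hospitalisation criterion for a serious adverse event is inconsistent within Protocol 12.1, and between Protocol 12.1 and SAP 4.5.3

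*Protocol*

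**What the plan says.** Protocol 12.1 (Amendment 2) lists the outcomes that make an event serious. The hospital bullet reads "Hospitalization (unplanned hospital stay) or prolongation of existing hospitalization". The section closes with an exemption: "Planned hospitalization or surgery for a condition present prior to the participant's enrollment in the study will not meet the definition of an SAE". Between the two stands an important-medical-event clause, under which events that do not "require hospitalization may be considered serious adverse events when, based on appropriate medical judgment, they may jeopardize the subject" and meet a further condition about intervention.

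SAP 4.5.3 gives its own definition. Its hospital bullet is "Requires in-patient hospitalization or prolongation of existing hospitalization", with no mention of planned or unplanned. It adds "Hospitalization for elective treatment or a pre-existing condition that did not worsen during the clinical investigation is not considered an AE". It has an important-medical-event clause too, under which such events "may be considered SAEs only when they jeopardize the health of the patient" or need intervention to prevent a listed outcome. It ends with a default: "If there is any doubt whether the information constitutes an SAE, the information is treated as an SAE in this study".

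Protocol 12 defines an AE broadly, as "any untoward clinical occurrence in a patient administered a pharmaceutical drug product", and has seriousness recorded on source documents and CRFs during the study. Protocol 12.4 requires every SAE to be reported within 24 hours. SAP Table 20 and Listing 17 present serious treatment-emergent events.

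**The concern.** Safety and tolerability are the primary objective, and serious-event incidence is one of the main ways of reporting them. Whether an admission makes an event serious should not depend on which sentence the investigator or programmer reads.

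The admissions at issue are the scheduled ones. Over several years of open-label treatment, a condition that emerges slowly may be worked up by appointment and admitted by arrangement, not as an emergency. A site that takes the protocol bullet at face value would not flag such an admission. The event would then miss the 24-hour report and Table 20, unless the investigator chose to use the important-medical-event clause.

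The reference point for a pre-existing condition matters too. If enrolment means enrolment in Study 304, a condition that began on retigabine in Study 302 already counts as present beforehand, and the protocol exemption contains no test for later worsening.

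**Working it through.** No arithmetic applies. The documents give no SAE or hospitalisation rate, and Protocol 11.3 declares sample size not applicable. The check is to apply each wording to the same types of admission, using the hospitalisation criterion alone.

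| Admission | 12.1 bullet | 12.1 closing sentence | SAP 4.5.3 |
|---|---|---|---|
| (a) Unplanned, condition arising in 304 | Met | Not exempted | Met |
| (b) Planned, condition arising in 304 | Not met | Not exempted | Exempted if elective treatment stands alone as a ground; met if the phrase means elective treatment of a pre-existing condition |
| (c) Planned, condition present before enrolment that then worsened | Not met | Exempted | Met, unless the stay is elective |
| (d) Unplanned, pre-existing condition that did not worsen | Met | Not exempted | Exempted, and said not to be an AE |

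The wordings agree in (a) and differ in (b), (c) and (d).

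- **Within the protocol, (b) is the conflict.** If the bullet already excluded every planned stay, the closing sentence would add nothing. Its presence implies that planned stays for new conditions were meant to count.
- **Between the documents, (c) and (d) differ.** The SAP tests for worsening and the protocol does not. For (d), Protocol 12 says that manifestations present before the study do not prompt an AE report to health authorities. That narrows the gap but does not change the seriousness criterion.
- **The Study 302 case falls under (c).** Protocol 10.5 carries AEs ongoing at Visit 11 of Study 302 onto the 304 pages, so conditions that began on retigabine can be present at 304 enrolment. If the study in the closing sentence is 304, a planned admission for one of them is exempt even after worsening.
- **Other routes to seriousness remain open.** In (b), the important-medical-event clause can still apply in either document, and so can the SAP's default for doubtful cases. The two clauses are not identical: the SAP says such events count only under its conditions, but joins those conditions with *or*, where the protocol uses *and*.
- **This is not version lag.** SAP section 1 names Protocol Amendment 1 as its source. The serious-event text in section 12.1 of Amendment 1 is the same as in Amendment 2. The SAP therefore departs from its own source, while SAP 4.8 declares no changes.

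**The case against.** The strongest reply is that only the protocol wording operates. Investigators record seriousness on the CRF, Listing 11 carries a field for it, and the SAP shows no step that re-derives it from admission records. On that view SAP 4.5.3 merely restates a definition. The two protocol sentences can also be reconciled by letting the closing sentence explain what an unplanned stay means. This stands in part: the SAP text is unlikely to reclassify events by itself, and the live problem is mainly inside 12.1. But the reconciling reading is not written down, and a site that reads the bullet literally has no doubt to resolve. The SAP's default for doubtful cases is also in a document that sites do not report from.

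Three stronger inferences are tempting, and the documents do not support them.

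- *A reader might infer that planned admissions for on-treatment conditions can never be SAEs.* The closing sentence of 12.1 does not exempt them, and the important-medical-event clause and the SAP's default can both bring them in.
- *A reader might infer that the SAP removes the condition itself from the AE data.* Its sentence concerns the hospitalisation. A new disorder on treatment is still an AE under Protocol 12 and goes into the treatment-emergent summaries. Worsening of a condition carried over from Study 302 is also treatment-emergent under Protocol 11.2.
- *A reader might infer a particular under-count, for instance of urinary events.* Protocol 10.3.4 sends some urinalysis findings for urological evaluation but mentions no admission. AUA and PVR results have their own tables (35 to 41), which do not depend on seriousness. No rate is available from which to calculate.

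**Conclusion.** The inconsistency is real and should be corrected. On a literal reading, a planned admission for a condition that arose on retigabine does not meet the protocol's hospitalisation criterion, although the closing sentence of the same section implies that it should. What is at risk is the serious flag, and with it the 24-hour report, Table 20 and Listing 17; recording of the underlying AE is not at risk.

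The size cannot be estimated from the documents. It depends on how often such admissions occur, how literally sites read the bullet, and how often the other routes to seriousness are used. The Study 302 point rests on reading the study in the exemption as 304, which is the plain sense of a 304 protocol but is not spelled out.

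**What to change.** Use one definition in both documents.

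- **Protocol 12.1:** delete the parenthesis that restricts the hospital bullet to unplanned stays. State that an adverse event requiring in-patient admission, or prolonging an existing stay, is serious. Tying the rule to an adverse event keeps out elective admissions with nothing untoward behind them. Limit the closing exemption to admissions planned for a condition that was present before the first retigabine dose and has not worsened since. That dose always falls in Study 302, because everyone who enters 304 is titrated to retigabine by the end of its Transition phase (Protocol 7.1), so the text should name Study 302, including Transition.
- **SAP 4.5.3:** repeat that text or cross-refer to it, and reword the exclusion so that an exempt admission is not an SAE, instead of not an AE. Align the important-medical-event wording at the same time. If any difference from the protocol is kept, declare it in SAP 4.8.

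The cost is a few sentences in each document and some additional SAE reports. Their number cannot be predicted from what the documents give.
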